3.10 Vaccine Development Strategy

A phase I clinical trial at a disease-endemic area (the MRC/Uganda Virus Research Unit, Entebbe) is planned following the ChAdOx1 RVF trial in Oxford. The optimal dose of ChAdOx1 RVF will be determined following the Oxford and Ugandan trials and, provided there are no safety concerns, phase II studies will be conducted in Uganda and Kenya.

4. OBJECTIVES AND ENDPOINTS

The number of volunteers has been chosen to generate adequate safety and immunogenicity data to meet these objectives, whilst minimising the number of volunteers exposed to a new vaccination regimen.

4.1 Primary Objective

To assess the safety and tolerability of ChAdOx1 RVF in healthy adult volunteers.

4.1.1 Primary Outcome Measures

The specific endpoints for safety and reactogenicity will be actively and passively collected data on adverse events.

The following parameters will be assessed for all study groups

- Occurrence of solicited local reactogenicity signs and symptoms for 7 days following the vaccination
- Occurrence of solicited systemic reactogenicity signs and symptoms for 7 days following the vaccination
- Occurrence of unsolicited adverse events for 28 days following the vaccination
- Change from baseline for safety laboratory measures
- Occurrence of serious adverse events during the whole study duration

Volunteers will undergo clinical follow up for a further 90 days following completion of the vaccination regimen. SAEs will be collected throughout the study. The duration of follow up reflects the desire to obtain safety data with the first use of ChAdOx1 RVF in humans.

4.2 Secondary Objective

To assess the cellular and humoral immunogenicity of ChAdOx1 RVF in healthy adult volunteers.

4.2.1 Secondary Outcome Measures

Measures of immunogenicity to the ChAdOx1 RVF vaccine may include:

- ELISA to quantify antibodies to GnGc proteins
- RVFV neutralising antibody titres
- Ex vivo ELISpot and flow cytometry responses to GnGc

Other exploratory immunology may be carried out in collaboration with other specialist laboratories, including laboratories outside of Europe. This would involve transfer of serum/plasma and/or peripheral blood

mononuclear cells (PBMC), but samples would be anonymised. Volunteers will be asked for their consent for this before enrolment.

5. STUDY OVERVIEW

This is a first-in-human, open-label, dose escalation, phase I clinical trial to assess the safety and immunogenicity of the candidate ChAdOx1 RVF vaccine in healthy volunteers aged 18-50. The vaccine will be administered intramuscularly.

Volunteers will be recruited and vaccinated at the CCVTM, Oxford. There will be 3 study groups and a total of 15 volunteers will be enrolled (table 2). The sequence of enrolment is described in section 7.4.2.2. Volunteers will be initially recruited into Group 1 and subsequently into Groups 2 and 3 following interim clinical safety reviews (see section 7.4.2). Volunteers will be allocated to a study group by selecting eligible volunteers for enrolment following screening.

5.1 Rationale for Selected Doses

Doses to be administered in this trial have been selected on the basis of clinical experience with the ChAdOx1 adenovirus vector expressing different inserts and similar adenovirus vectored vaccines (eg. ChAd63).

A first-in-human dose escalation study using the ChAdOx1 vector encoding an influenza antigen (FLU004), safely administered ChAdOx1 NP+M1 at doses ranging from 5×10^8 to 5×10^{10} vp. Subsequent review of the data identified an optimal dose of 2.5×10^{10} vp balancing immunogenicity and reactogenicity. This dose has subsequently been given to over 175 volunteers in numerous larger phase 1 studies at the Jenner Institute (FLU005, TB034 VANCE01, ADVANCE and VAC067) and ChAdOx1 vectored vaccines have thus far demonstrated to be very well tolerated. The vast majority of AEs have been mild-moderate and there have been no SARs until this date in these studies.

Other ChAdOx1 vectored vaccines have been given at doses up to 5×10^{10} vp (MERS001, VAMBOX, CHIK001 and nCoV-19) whilst a different simian adenovirus vector (ChAd63) has been safely administered at doses up to 2×10^{11} vp with an optimal dose of 5×10^{10} vp, balancing immunogenicity and reactogenicity.

As this is a first-in-human assessment of the RVFV GnGc antigenic insert, the first dose of ChAdOx1 RVF proposed in this study (5×10^9 vp) is therefore 10 fold less than the expected tolerable dose of ChAdOx1 RVF (5×10^{10} vp). Doses will be gradually increased aiming to provide an optimal dose of ChAdOx1 RVF considering the tolerability, reactogenicity and immunogenicity profiles.

5.2 Study Groups

Table 2. Study Groups

Group	Single Dose ChAdOx1 RVF	Route
Group 1 (n=3)	5 x 10 ⁹ vp	IM
Group 2 (n=6)	2.5 x 10 ¹⁰ vp	IM
Group 3 (n=6)	5 x 10 ¹⁰ vp	IM

5.2.1 Duration of study

The total duration of the study will be 12 weeks from the day of enrolment for all volunteers.

5.2.2 Definition of Start and End of Trial

The start of the trial is defined as the date of the first vaccination of the first volunteer. The end of the trial is the date of the last visit of the last volunteer.

5.3 Potential Risks for volunteers

The potential risk to participants is considered as low. The potential risks are those associated with phlebotomy and vaccination. In general, recombinant adenoviral vectors are safe. Similar vaccines encoding different antigens have been given to several thousand volunteers (including children) with a good safety profile.

Phlebotomy:

The maximum volume of blood drawn over the study period (approximately 300mL) should not compromise these otherwise healthy volunteers. There may be minor bruising, local tenderness or pre-syncope symptoms associated with venepuncture, which will not be documented as AEs if they occur.

Vaccination:

ChAdOx1 RVF has not been used in humans before and therefore will be initially administered at the lower dose of 5 x 10⁹ vp before progressing to the higher doses of 2.5 x 10¹⁰ and 5 x 10¹⁰ vp in Groups 2 and 3. Expected risks from vaccination include local effects such as pain, redness, warmth, swelling, tenderness or itching. Systemic reactions that could potentially occur following immunisation with a recombinant adenovirus vaccine include a flu-like illness with feverishness, fatigue, malaise, arthralgia, myalgia and headache.

As with any vaccine, Guillain-Barré syndrome or immune-mediated reactions that can lead to organ damage may occur, but this should be extremely rare. Serious allergic reactions including anaphylaxis could also occur and for this reason volunteers will be vaccinated in a

clinical area where Advanced Life Support trained physicians, equipment and drugs are immediately available for the management of any serious adverse reactions (SAR).

Thrombosis with Thrombocytopenia:

In April 2021, MHRA and JCVI conducted a review of extremely rare reports of cerebral venous sinus thrombosis (and thrombosis of other major veins) with concurrent thrombocytopenia occurring after vaccination with ChAdOx1 nCoV-19 in the national COVID-19 vaccination programme. The potential mechanism of these events, and whether they are related to the ChAdOx1 viral vector or to the SARS-CoV-2 spike protein, is yet to be determined. Estimates of incidence of thrombosis with thrombocytopenia following ChAdOx1 nCoV-19 vaccination vary and may change further as more cases are gathered and case definitions are finalised; current UK estimates are of cases occurring after less than 1 in 100,000 prime vaccinations.

On the basis of their ongoing scientific review the UK Medicines Healthcare Regulatory Agency have concluded: “the evidence of a link with vaccination and COVID-19 is stronger, but more work is still needed”(62). The European Medicines Agency concluded that unusual blood clots with low blood platelets should be listed as very rare side effects of this vaccine. Both agencies concluded that there wasn’t enough evidence at present to say what the risk factors (e.g. age, gender, or other medical conditions) might be for having one of these rare clotting problems. Although the MHRA have received a higher number of reports from younger adults than older individuals. Cases of thrombosis with thrombocytopenia have also been reported after COVID-19 Vaccine Janssen, an adenovirus serotype 26 vectored spike-protein based COVID-19 vaccine. The EMA has also conducted a review of these cases and concluded there is a likely causal relationship with the Janssen vaccine(63).

Thrombosis with thrombocytopenia syndrome has not previously been reported following the use of live oral adenovirus serotype 4 and serotype 7 adenovirus vaccines in the United States, where these vaccines have been approved for vaccination of military personnel(64-66). Over 1.3 million doses have been administered between 2011 to 2018 with no reports of thrombosis following vaccination to the US CDC/FDA Vaccine Adverse Event Reporting System (VAERS) post-marketing passive vaccine safety monitoring database(66).

Both the MHRA and EMA have confirmed that the evidence to date does not suggest that the COVID-19 Vaccine AstraZeneca causes venous thromboembolism *without* a low platelet count(62, 67).

All volunteers will be provided with this information via the study information booklet and will be kept updated should further information become available. They will also be specifically counselled on symptoms that could be warning signs of serious clotting events, as per public health advice being given to people receiving ChAdOx1 nCoV-19.

Potential interaction with other adenoviral vectored vaccines:

The ChAdOx1 vector used in the ChAdOx1 RVF experimental vaccine is the same as that used in the Oxford AstraZeneca and similar to the one used in the Janssen (Johnson and Johnson) COVID-19 vaccines (Adenovirus 26). There is a theoretical risk that receiving the experimental ChAdOx1 RVF vaccine may reduce the benefit of subsequent administrations of certain vaccines such as the Janssen (Johnson & Johnson) or the AstraZeneca COVID-19 vaccines. This may be more likely to happen if the vaccines are given at short intervals. However, the immune response to the AstraZeneca COVID-19 vaccine was not affected in a study of individuals who received a previous ChAdOx1-vectored vaccine for a non-spike transgene at least one year earlier(68, 69).

Other studies suggest that an interval of three months between administrations of two adenoviral vectored vaccines reduces the risk of this interference(70-74). For this reason, we will enrol participants who have been vaccinated with an mRNA Covid vaccine or will have their NHS Covid vaccine offer at least three months after the ChAdOx1 RVF vaccine. No such theoretical interference will be expected with mRNA or protein COVID-19 vaccines (such as Moderna, Pfizer, Novavax) and these can be given at least 2 weeks before or after the ChAdOx1 RVF.

5.4 Known Potential Benefits

Volunteers will not benefit directly from participation in this study. However, it is hoped that the information gained from this study will contribute to the development of a safe and effective RVFV vaccine regimen. The only benefits for participants would be information about their general health status.

6. RECRUITMENT AND WITHDRAWAL OF TRIAL VOLUNTEERS

6.1 Volunteers

Volunteers may be recruited by use of an advertisement +/- registration form formally approved by the ethics committee(s) and distributed or posted in the following places:

- In public places, including buses and trains, with the agreement of the owner/proprietor.
- In newspapers or other literature for circulation.
- On radio via announcements.
- On a website or social media site operated by our group or with the agreement of the owner or operator (including on-line recruitment through our web-site).
- By e-mail distribution to a group or list only with the express agreement of the network administrator or with equivalent authorisation.
- By email distribution to individuals who have already expressed an interest in taking part in any clinical trial at the Oxford Vaccine Centre.
- On stalls or stands at exhibitions or fairs.
- Via presentations (e.g. presentations at lectures or invited seminars).
- Direct mail-out: This will involve obtaining names and addresses of adults via the most recent Electoral Roll. The contact details of individuals who have indicated that they do not wish to receive postal mail-shots would be removed prior to the investigators being given this information. The company providing this service is registered under the relevant data protection legislation. Investigators would not be given dates of birth or ages of individuals but the list supplied would only contain names of those aged between 18-50 years (as per the inclusion criteria).
- Oxford Vaccine Centre databases: We may contact individuals from databases of groups within the CCVTM (including the Oxford Vaccine Centre database) of previous trial participants who have expressed an interest in receiving information about all future studies for which they may be eligible.

6.2 Informed consent

All volunteers will sign and date the informed consent form before any study specific procedures are performed. The information sheet will be made available to the volunteer at least 24 hours prior to the screening visit. At the screening visit, the volunteer will be fully informed of all aspects of the trial, the potential risks and their obligations. The following general principles will be emphasised:

- Participation in the study is entirely voluntary
- Refusal to participate involves no penalty or loss of medical benefits
- The volunteer may withdraw from the study at any time
- The volunteer is free to ask questions at any time to allow him or her to understand the purpose of the study and the procedures involved

- The study involves research of an investigational vaccine
- There is no direct benefit from participating
- The volunteer's GP will be contacted to corroborate their medical history. Volunteers will only be enrolled in the study if written or verbal information regarding the volunteer's medical history is obtained from the GP. This can either be via the study team accessing patient's electronic care summaries from local systems or by contacting the GP.
- The volunteer's blood samples taken as part of the study will be stored indefinitely and samples may be sent outside of the UK and Europe to laboratories in collaboration with the University of Oxford. These will be anonymised.

The aims of the study and all tests to be carried out will be explained. The volunteer will be given the opportunity to ask about details of the trial, and will then have time to consider whether or not to participate. If they do decide to participate, they will sign and date one consent form from which copies are made, one for them to take away and keep, and one to be stored in the case report form (CRF) – this is a paper or electronic document used to collect data relating to a particular volunteer. These forms will also be signed and dated by the Investigator.

Whilst the COVID-19 pandemic continues to affect the UK volunteers will be provided with an information sheet detailing the precautions being taken. They will be asked to agree to abide by the most recent UK government guidance on self-isolation, testing and social distancing.

6.3 Inclusion and exclusion criteria

This study will be conducted in healthy adults, who meet the following inclusion and exclusion criteria:

6.3.1 Inclusion Criteria

The volunteer must satisfy all the following criteria to be eligible for the study:

1. Healthy adults aged 18 to 50 years
2. Able and willing (in the Investigator's opinion) to comply with all study requirements
3. Willing to allow the investigators to discuss the volunteer's medical history with their General Practitioner or access this medical history electronically
4. For females only, willingness to practice continuous effective contraception (see below) for at least 3 months from the final vaccination procedure and a negative pregnancy test on the day(s) of screening and vaccination
5. Agreement to refrain from blood donation during the course of the study
6. Able to provide written informed consent

6.3.2 Exclusion Criteria

The volunteer may not enter the study if any of the following apply:

1. Participation in another research study involving receipt of an investigational product in the 30 days preceding enrolment, or planned use during the study period
2. Prior receipt of an investigational vaccine likely to impact on interpretation of the trial data.
3. Prior receipt of any vaccines administered ≤ 30 days before enrolment and/or planned receipt of a vaccine ≤ 30 days after enrolment EXCEPT for protein, RNA (or other non-adenovirus based) COVID-19 vaccinations which may be given within 14 days of the trial vaccine.
4. Receipt of a recombinant simian adenoviral vaccine prior to enrolment
5. Planned receipt of another adenoviral vectored vaccine (e.g. Oxford/Astrazeneca or Janssen COVID-19 vaccines) within 90 days after the vaccination with the ChAdOx1 RVF
6. Administration of immunoglobulins and/or any blood products within the three months preceding the planned administration of the vaccine candidate
7. Any confirmed or suspected immunosuppressive or immunodeficient state, including HIV infection; asplenia; recurrent, severe infections and chronic (more than 14 days) immunosuppressant medication within the past 6 months (inhaled and topical steroids are allowed)
8. COVID-19 infection diagnosed in the community in the 28 days prior to enrolment
9. Any main covid-19 symptom within 28 days of enrolment:
 - a. Fever (subjective or ≥ 37.8)
 - b. New continuous cough
 - c. Loss of sense of smell
 - d. Loss of sense of taste
10. Clinical suspicion of acute COVID-19 in the 28 days prior to enrolment
11. History of allergic disease or reactions likely to be exacerbated by any component of the vaccine
12. Any history of hereditary angioedema, acquired angioedema, or idiopathic angioedema.
13. Any history of anaphylaxis in relation to vaccination
14. Pregnancy, lactation or willingness/intention to become pregnant during the study
15. History of cancer (except basal cell carcinoma of the skin and cervical carcinoma in situ)
16. History of serious psychiatric condition likely to affect participation in the study
17. Bleeding disorder (eg. factor deficiency, coagulopathy or platelet disorder), or prior history of significant bleeding or bruising following IM injections or venepuncture
18. Any other serious chronic illness requiring hospital specialist supervision
19. Suspected or known current alcohol abuse as defined by an alcohol intake of greater than 42 units every week

20. Suspected or known injecting drug abuse in the 5 years preceding enrolment
21. Seropositive for hepatitis B surface antigen (HBsAg)
22. Seropositive for hepatitis C virus (antibodies to HCV)
23. Any clinically significant abnormal finding on screening biochemistry or haematology blood tests or urinalysis
24. Any other significant disease, disorder or finding which may significantly increase the risk to the volunteer because of participation in the study, affect the ability of the volunteer to participate in the study or impair interpretation of the study data
25. Inability of the study team to contact the volunteer's GP (or access summary care record, if available) to confirm medical history and safety to participate
26. Prior natural exposure to RVFV as determined by seropositivity for RVFV antigens by ELISA and neutralizing antibody assay (serology will be requested at the discretion of the investigator)
27. History of confirmed major thrombotic event (including cerebral venous sinus thrombosis, deep vein thrombosis, pulmonary embolism), history of antiphospholipid syndrome, or history of heparin induced thrombocytopenia

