6.3.5 Criteria for postponement of vaccination

The following events constitute contraindications to administration of the vaccine at that point in time; if any one of these events occurs at the time scheduled for vaccination, the subject may instead be vaccinated at a later date following resolution and within the window of screening procedures (defined in section 7.4.1), or withdrawn at the discretion of the Investigator.

- Acute disease at the time of vaccination. Acute disease is defined as the presence of a moderate or severe illness with or without fever.
- Temperature of >37.5°C (99.5°F) at the time of vaccination.

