7.4.2 Day 0: Enrolment and Vaccination Visit

Volunteers will not be considered enrolled in the study until they have received a vaccine. Before vaccination, the eligibility of the volunteer will be reviewed including re-checking informed consent and willingness to be vaccinated. Pulse, blood pressure and temperature will be observed and if necessary, a medical history and physical examination may be undertaken to determine need to postpone vaccination depending on criteria listed in section 6.3.5. Vaccinations will be administered as described below.

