7.4.2.1 Vaccinations

Before each vaccination, the on-going eligibility of the volunteer will be reviewed. All vaccines will be administered intramuscularly according to SOP VC002 Vaccination as described below in section 8.4 and the vaccine dilution SOP when required. The injection site will be covered with a sterile dressing and the volunteer will stay in the CCVTM for observation, in case of immediate adverse events. Observations will be taken 30 minutes after vaccination (+/- 5 minutes) and the sterile dressing removed and injection site inspected. Observations will also be taken at 60 minutes (+/- 10 minutes) before the volunteer leaves. An oral thermometer, tape measure and diary card (paper or electronic) will be given to each volunteer, with instructions on use, along with the emergency 24 hour telephone number to contact the on-call study physician if needed.

Diary cards will collect information on the timing and severity of the following solicited AEs:

Table 3. Solicited AEs as collected on post vaccination diary cards

Local solicited AEs	Systemic solicited AEs
Pain	Fever
Redness	Feverishness
Warmth	Joint pains
Itch	Muscle pains
	Fatigue
	Headache
	Nausea
	Malaise

Volunteers will be instructed on how to self-assess the severity of these AEs. There will also be space on the diary card to self-document unsolicited AEs, and whether medication was taken to relieve the symptoms.

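### Exclusion criterion 3 permits a non-adenoviral COVID-19 vaccine less than 14 days from the trial vaccine; section 5.3 makes two weeks the minimum gap

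*Protocol*

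**What the plan says.** Criterion 3 in Protocol section 6.3.2 excludes a volunteer who received any vaccine in the 30 days before enrolment. It also excludes "planned receipt of a vaccine ≤ 30 days after enrolment EXCEPT for protein, RNA (or other non-adenovirus based) COVID-19 vaccinations". It then describes the exempt products as "COVID-19 vaccinations which may be given within 14 days of the trial vaccine".

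Section 5.3, in the part on interaction with other adenoviral vaccines, says of mRNA and protein COVID-19 vaccines that "these can be given at least 2 weeks before or after the ChAdOx1 RVF".

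Section 7.4.2 puts both rules on the same clock: "Volunteers will not be considered enrolled in the study until they have received a vaccine". Enrolment is therefore day 0, the day of the trial vaccine.

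**The concern.** One passage permits a COVID-19 vaccine inside 14 days and the other treats 14 days as the least acceptable gap. Staff who screen volunteers work from the numbered criteria, so the wording of criterion 3 is what would be applied.

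What is at stake is attribution of reactions. Solicited local and systemic events over 7 days are primary outcomes (section 4.1.1), and the trial has no control group and dose groups of 3, 6 and 6. A second reactogenic vaccine on or near day 0 could produce the very symptoms listed in Table 3. The solicited holding rules in section 9.9.1 are met when two participants have a grade 3 solicited event starting on day 0 or 1. Unlike the unsolicited rule, they carry no relatedness condition. Restarting after a hold requires a substantial-amendment request to the regulator.

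**Working it through.** The protocol gives no figure to reproduce, so the check is to lay the two rules on one time scale.

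**Inputs.** Let k be the day of a non-adenoviral COVID-19 vaccine minus day 0, for k = -30 to +30 (61 whole days).

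- Section 5.3 permits |k| ≥ 14. That is 17 days on each side, 34 in all.
- Criterion 3, exemption read as a ceiling: permits |k| ≤ 14, which is 29 days.
- Criterion 3, exemption read as 'even within 14 days': permits all 61.

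**Comparison**

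| Gap (days) | Offsets | Section 5.3 | Criterion 3, ceiling | Criterion 3, 'even within' |
|---|---|---|---|---|
| 0–13 | 2×13 + 1 = 27 | not permitted | permitted | permitted |
| 14 | 2 | permitted | permitted | permitted |
| 15–30 | 2×16 = 32 | permitted | barred | permitted |
| over 30 | off the grid | permitted | permitted | permitted |

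The conflict covers 27 offsets under either of these readings, and 27 + 32 = 59 under the ceiling reading.

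**Where the 27 offsets touch safety data**

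- *Solicited window, days 0–6 (section 9.9).* COVID-19 doses on k = 0 to 6 fall inside it: 7 offsets, from day 0 onward. An earlier dose overlaps if its reactions last D days and -(D-1) ≤ k ≤ -1, which adds D-1 offsets: 1, 2 or 6 for D = 2, 3 or 7. D is my assumption.
- *Holding window, onset on day 0 or 1 (section 9.9.1).* If onset comes 0 to L days after the COVID-19 vaccine, then k runs from -L to 1, which is L + 2 offsets: 2, 3 or 4 for L = 0, 1 or 2. L is my assumption.
- *Under section 5.3.* The nearest doses are k = -14 and k = +14, so no offset reaches either window for any D or L used.
- *Unsolicited window.* The primary outcome is "Occurrence of unsolicited adverse events for 28 days following the vaccination". Section 5.3 still allows COVID-19 doses there: k = 14 to 27 (14 offsets), or 14 to 28 (15) if day 28 is included.

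**Existing safeguards**

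- Exclusion 9, "Any main covid-19 symptom within 28 days of enrolment", lists fever, cough and loss of smell or taste. Of the 8 systemic solicited terms in Table 3 it reaches 2 (fever and feverishness) and leaves 6.
- Section 6.3.5 postpones vaccination for a temperature above 37.5°C or for acute disease: "Acute disease is defined as the presence of a moderate or severe illness with or without fever". Mild, afebrile reactions pass.
- Both checks act before dosing. Neither covers a COVID-19 vaccine given later on day 0 or on days 1 to 6.
- Section 9.4 has causality assessment consider concomitant therapy, but causality does not enter the solicited holding count.

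**The case against.** The strongest reply is that criterion 3 is simply misworded. Its phrase is an exception to a 30-day bar, and an exception that shortens the bar to 14 days is a natural intent that would agree exactly with section 5.3. On that reading nothing conflicts. This may well be what the sponsor meant, but the printed words grant permission inside the 14 days. If it is a slip, it is a slip in an entry rule and needs correcting.

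It can also be said that section 5.3 is a risk narrative and not an eligibility rule. That is so, and its minimum gap is implied by permissive wording. It is nevertheless the only other statement of the interval in the protocol.

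The consequences are also contingent. A site would have to follow criterion 3 against section 5.3, a volunteer would have to be vaccinated close to day 0, and a hold would need two grade 3 events. Dose escalation rests on case review by the Chief Investigator and the Local Safety Monitor, and the internal review after a hold must weigh other possible causes. These points limit the harm. They do not stop the reactions entering the solicited tabulations or triggering the hold. Finally, day offsets say nothing about frequency, and section 5.3 itself does not keep COVID-19 vaccines out of the unsolicited data. Both points stand.

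**Conclusion.** The inconsistency is real and should be fixed. As printed, gaps of 0 to 13 days are permitted by criterion 3 and not by section 5.3. This needs no assumption beyond taking the words as they stand. For gaps of 15 to 30 days, conflict arises only if the exemption is a ceiling. The direct contradiction concerns mRNA and protein vaccines. For other non-adenoviral COVID-19 vaccines section 5.3 states no spacing, which is a gap and not a contradiction.

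The practical difference between the passages lies in the 7-day solicited outcome and the day 0–1 holding window. The counts for COVID-19 doses before day 0 rest on assumed reaction durations and onset lags, and the entry checks would screen some of those volunteers. The number of volunteers affected is unknown and could be zero.

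**What to change.** Reconcile criterion 3 and section 5.3 so that both give the same interval before the trial vaccine, the same interval after it, and the same COVID-19 vaccine types. The wording should make clear whether the stated number of days is a minimum or a maximum gap. Which interval applies is for the sponsor to decide.

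The cost is a wording amendment to one or both passages, with the associated approvals paperwork. Depending on the interval chosen, some vaccination visits might have to be re-timed. Section 7.4.1 allows screening up to 90 days before vaccination, which leaves some room for that. No change to sample size or analysis follows.
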